We hypothesize that: 1) our peri-operative intervention will be feasible and safe to undertake within a clinical setting; 2) we will enrol adequate numbers to justify a larger trial; and that 3) our study protocol will provide meaningful information with high response rate and low attrition after 3 months.

Justification

Inguinal hernia repair is one of the most common surgeries performed globally, with more than 20 million performed each year.[1] Not only does this huge number of surgeries have a substantial direct economic burden on healthcare systems, there is also indirect impact from time off work and decreased productivity due ongoing post-surgical pain requiring extended time spent on modified duties. It is estimated that approximately 15% of patients undergoing inguinal hernia repair will experience persistent post-surgical pain that could last months to years.[2, 3] Furthermore, current clinical guidelines for return to work and activity after inguinal hernia repair are inconsistently informed by evidence, highly variable, and outdated.

[4] Forbes et al (2012) found that the average patient undergoing inguinal hernia repair experiences more than 40 days of short-term disability despite indications that earlier return to activity is safe (i.e. will not lead to repair failure) and likely beneficial for reducing chronic pain and disability.[4]

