Sample - We will recruit patients referred to general surgery for an elective inguinal hernia repair within Alberta Health Services – Fort Saskatchewan Community Hospital ([name] clinic). Patients meeting the inclusion criteria will be randomized 1:1 to either undergo 6 weeks of prehabilitation exercises + post-surgical follow-up or else usual care. Inclusion criteria include: 1) scheduled to undergo first-time inguinal hernia repair surgery after a physical examination identified signs and symptoms consistent with inguinal hernia (direct or indirect hernia); 2) willingness to participate in a targeted perioperative exercise program; 3) 18+ years of age; 4) no medical contraindications to participation in exercise; and 5) employed full-time and required to lift at least 10kg at work. Specific contra-indications that will be screened for include associated medical conditions that preclude exercise. This includes uncontrolled medical conditions including diabetes, hypertension, vertigo, congestive heart failure, chronic obstructive pulmonary disease, intra-abdominal ascites, or pre-existing malnutrition. We will also screen for previous recurrence of hernia, use of narcotics, bone and joint conditions of the spine or extremities, or history of other abdominal surgeries, which will be exclusionary criteria for the study. Exclusion criteria include: 1) previous inguinal hernia; and 2) Body Mass Index >35 since morbidly obese patients experience more surgical complications.[13]

Sample Size - Since this is a pilot study evaluating feasibility of our intervention and evaluation protocols, we will aim to enrol 30 patients. We will randomize 15 to both the intervention and control groups. Thirty participants has been deemed acceptable to yield confidence intervals whose lower limits can help define the range of plausible values for a subsequent power analysis.[14] This will also provide adequate estimates of enrolment, follow-up rates, information on timing, and variance in our measurement protocol to inform a subsequent randomized controlled trial of the intervention.

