Data Collection Procedures – Activities and timing of data collection are outlined in the attached document entitled 'Perioperative Rehabilitation Activity and Data Collection Protocol for Inquinal Hernia ' We will enrol patients undergoing inguinal hernia repair surgery. Participation will be voluntary, and patients will be informed of the study 8 weeks before their scheduled surgery. Once scheduled and enrolled, patients will be randomized by a research team member using Redcap. Schedule will be developed by a statistician not involved in the randomization. Participants in the intervention group will be referred to the University of Alberta's Student Physical Therapy clinic where they will undertake the pre-operative exercise and education program. The education program will include selfmanagement, expectations about the surgical and recovery process as well as quidelines for post-operative exercises. After surgery, participants in the intervention group will undergo a clinical evaluation after surgery, with the physiotherapists who will guide post-operative exercises and modify as needed. The exercises will avoid all contraindications in the acute postsurgical period, including no lifting >10kg for the first 4 weeks. The study will not impact scheduling of surgery or typical procedures. Participants in the intervention group will be booked for a short assessment with the general surgeon, remotely, to evaluate progress.

COVID-19 Implications - Since inguinal hernia repair operations have continued to be conducted despite the pandemic and physiotherapy clinics are operating following public health recommendations, unless these interventions are out on hold we will conduct this study within the typical clinical care pathway. After an initial in-person evaluation where masks will

be worn and all exercise and testing equipment is sterilized after use, all interventions will be conducted in accordance with the COVID-19 specific requirements from Public Health authorities. Telehealth options for the interventions will be available.

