Clinical outcomes will be collected at baseline, before surgery, and following the post-surgical intervention by a researcher not involved in the delivery of the intervention. Persistent post-surgical will be defined as pain lasting longer than 3 months post-surgery as per the IASP definition.[15] We will measure pain intensity ratings on a 0-10 Numeric Pain Scale. We will also measure pain-related disability using the Pain Disability Index and SF-12 measures. Lastly, after the operation we will administer the hernia-specific Carolinas Comfort Scale (CCS).[16] The CCS is a widely used hernia-specific patient reported outcome measure that focuses on mesh-related symptoms.[17] We will also measure quality of life and factors linked to chronic pain such as coping strategies, catastrophizing and Kinesiophobia.

Safety and adverse effects – At the weekly sessions, we will as about both exercise completion as well as any symptoms or adverse events experienced. These will be documented. Any post-surgical complications severe enough to warrant referral to the surgeon or ultrasound imaging will also be tracked. Since the ultrasounds are only being done to rule out hernia recurrence as part of routine clinical care, this will be done and interpreted by a radiologist. All patients will also undergo a consult with the surgeon at 1-week, 1-month, and 3-month follow-up as per usual practice.

Plan for Data Analysis

A sample size of 30 participants will yield confidence intervals whose lower limits can help define the range of plausible values for a subsequent power analysis program. This will guarantee the timely and on-budget completion of the study. All analyses will be conducted using STATA 14.2. Descriptive analysis will be used to report feasibility outcomes (e.g. recruitment rates, adherence, etc.) and identify trends of clinical outcomes. Feasibility targets will be evaluated as per the Appendix.

See Attached Study Protocol for the full list of references.

- 3.0 Describe procedures, treatment, or activities that are above or in addition to standard practices in this study area (eg. extra medical or health-related procedures, curriculum enhancements, extra follow-up, etc): The Prehab program discussed above that we are studying is in addition to the standard surgical practices in this study area.

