Specific physical complications could arise before the operation is performed or after surgery. Prior to surgery, the patient may experience more pain in the hernia site as well as normal pain associated with exercise, they may notice worsening of the size of the hernia, and there is a very small chance of hernia incarceration (i.e. herniated tissue becomes trapped and cannot easily be moved back into place – typically occurs in less than 1% (0.18% to 0.79%) of hernia cases). Increased symptoms or size of the hernia will be monitored, and exercises will be modified if the symptoms become intolerable to the participant. Hernia incarceration is an acute painful episode that will require a visit with the surgeon.

In the post-operative phase, patients may experience postoperative pain, opening of the superficial wound from potential hazards associated with exercising (i.e. falling, etc.). However, studies on the force required to cause hernia rupture indicate the force is quite high and beyond those generated during the exercises prescribed. If a participant experiences pain associated with our exercise intervention, we will modify or stop the aggravating exercises after consultation with the surgeon.

Exercise prior to surgery requires mental concentration and participants may feel psychologically or emotionally stressed or fatigue. Since they are in a research study, there is always some risk of social risk through loss of privacy.

4.0 * Describe how you will manage and minimize risks and discomforts, as well as mitigate harm:

The exercise programs will be monitored by experienced physical therapists and kinesiologists who will track patient progress. Since the exercise program is overall low intensity exercise, we do not anticipate many injuries or adverse events. However, if patients begin experiencing problems, the therapists will advise on alterations to make the exercises less intensive or recommend that the program be stopped. The therapists will also be available should more serious adverse events occur such as injury or other related complication. If this occurs, the therapists will advise on self-management strategies for the injury or initiate follow-up with the surgeon.

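### Routine adverse-event enquiry is described only at the program's weekly sessions, so events before surgery (other than pain) and milder events have no control-arm reference collected the same way

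*Combined protocol and SAP*

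**What the plan says.** All references are to the Combined protocol and SAP.

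- **Hypothesis (section 2.1).** The first hypothesis is that "our peri-operative intervention will be feasible and safe to undertake within a clinical setting". No comparator, rate or margin is attached to it.
- **Sample (section 2.1).** Patients "will be randomized 1:1 to either undergo 6 weeks of prehabilitation exercises + post-surgical follow-up or else usual care". On numbers: "We will randomize 15 to both the intervention and control groups".
- **Who attends sessions (section 2.1, Data Collection Procedures and Intervention Description).** "Participants in the intervention group will be referred to the University of Alberta's Student Physical Therapy clinic". Sessions appear only as part of program delivery. There is one further contact: "Participants in the intervention group will be booked for a short assessment with the general surgeon, remotely, to evaluate progress".
- **Safety and adverse effects (section 2.1).** "At the weekly sessions, we will as about both exercise completion as well as any symptoms or adverse events experienced". The same paragraph adds that post-surgical complications leading to surgical referral or an ultrasound are tracked. It also says that every patient sees the surgeon 1 week, 1 month and 3 months after the operation, as is routine. Neither statement is limited to one arm.
- **Clinical outcomes (section 2.1).** Pain and other patient-reported outcomes are collected at baseline, before surgery and after the post-surgical program, also without limitation to one arm.
- **Expected harms (section 3.1, item 3.0).** Before surgery, patients may have more pain at the hernia, "they may notice worsening of the size of the hernia", and incarceration is possible but rare (0.18% to 0.79%).
- **Progression rule (Appendix 2, Adverse Events row).** Zero events means proceed; two or more means significant amendments. No arm, denominator or seriousness is given, and only the middle tier mentions a cause (re-injury). Measures in section 2.1 names serious adverse events as the feasibility outcome.

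**The concern.** The enquiry about events is asked together with exercise completion, which only people given the exercises can answer. Followed as written, the plan questions one arm about symptoms every week and describes no equivalent for the other, least of all before surgery.

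The harms listed in section 3.1 for that period can also arise in an unrepaired hernia with no program. A randomised control arm is the trial's internal source for that background rate, but it supplies one only if its events are collected in the same way.

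Two errors become possible. A harmless program could trip the Appendix 2 threshold on the natural course of the hernia. A true excess could be explained away as closer questioning. Safety is both a stated hypothesis and a progression criterion for the larger trial, so either error would carry forward.

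**Working it through.** **1. Plan's own figure.** 15 + 15 = 30, which agrees with the stated sample size. No power or precision target lies behind it, so nothing further can be reproduced.

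**2. What each arm is described as receiving.**

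| Source of event information | Intervention | Usual care |
|---|---|---|
| Weekly enquiry before surgery (6 weeks, once a week) | about 6 | none described |
| Extra remote surgeon assessment | yes | no |
| Surgeon consults at 1 week, 1 month, 3 months | yes; not said to be logged as study events | same |
| Tracking of severe post-surgical complications | yes | not limited to one arm |
| Pain at baseline, before surgery and after the post-surgical program | yes | not limited to one arm |

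Pain and severe post-surgical events therefore have some common basis. Hernia enlargement, incarceration before surgery and milder events do not.

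**3. What background events alone do to the Appendix 2 count.** Let *p* be the chance that a participant has at least one event unrelated to the program, and let n = 15. Then P(two or more participants) = 1 − (1 − p)^15 − 15p(1 − p)^14. Counting events rather than participants can only raise this.

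| p | Source | P(0) | P(1) | P(≥2) |
|---|---|---|---|---|
| 0.18% | incarceration, section 3.1 | 0.9733 | 0.0263 | 0.03% |
| 0.79% | incarceration, section 3.1 | 0.8878 | 0.1060 | 0.6% |
| 5% | assumed | 0.4633 | 0.3658 | 17% |
| 10% | assumed | 0.2059 | 0.3432 | 45% |
| 20% | assumed | 0.0352 | 0.1319 | 83% |

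For rare serious events the rule is barely affected. For common symptoms it can fail with no program effect.

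Which arm is counted also matters. With the same formula and n = 30, P(≥2) at 5%, 10% and 20% is 45%, 82% and 99%.

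**4. Effect of unequal detection (assumed figures).** Expected detected count = 15 × true risk × proportion captured. Full capture is assumed in the intervention arm.

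| True risk, both arms | Intervention | Controls, 25% captured | Controls, 50% captured |
|---|---|---|---|
| 10% | 1.5 | 0.375 | 0.75 |
| 20% | 3.0 | 0.75 | 1.5 |
| 30% | 4.5 | 1.125 | 2.25 |

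The documents give no capture rates. The direction needs only that weekly questioning finds more than routine consults do.

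**5. What equal enquiry would deliver.** At an assumed 20% in both arms, the expected counts become 3.0 and 3.0. For 3/15 against 3/15, each Wilson 95% interval runs from 0.0705 to 0.4519. The Newcombe limits for the difference are ±√[(0.20 − 0.0705)² + (0.4519 − 0.20)²] = ±0.283, or about −28 to +28 percentage points. Zero events in 15 still allows a true rate up to 1 − 0.05^(1/15) = 18% (one-sided 95%). Equal enquiry removes a bias and supplies a background rate; it does not let 30 patients demonstrate safety.

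**The case against.** The case on the other side has real substance.

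- **Unseen attachments.** Section 2.1 refers the timing of data collection to an attached document, and the Documentation section lists both that timeline and an Adherence and Adverse Events Form. Neither is in the file. They may schedule enquiry for controls, so it is a strong inference, not stated text, that only the intervention arm is asked. This stands.
- **Controls are not unobserved before surgery.** A reader might infer that usual-care patients are seen only at the three post-surgical consults, and that program harm cannot be separated from the hernia or the operation at all. The documents do not support that. Pain is collected at baseline and before surgery without limitation to one arm, and severe post-surgical complications are tracked. The gap concerns enlargement, incarceration before surgery and milder events.
- **No between-arm comparison is planned.** A reader might also infer a false excess of some definite size. The plan analyses feasibility outcomes descriptively and the Appendix uses a raw count, so any ratio rests on assumed capture rates for a contrast the plan never states. This stands; what remains is that the raw count has no background rate beside it.
- **Serious events are less exposed.** Section 3.1 says incarceration needs a surgeon visit, and 15 × 0.0018 to 15 × 0.0079 gives only 0.03 to 0.12 expected cases. Unequal detection matters mainly for milder events. But the Appendix row is not limited to serious ones.
- **Closer monitoring of exercising patients is reasonable.** It is, and nothing here argues for reducing it. A common enquiry can be added alongside it.

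**Conclusion.** The concern holds in a limited form. On the visible text, routine enquiry about events is described only at program sessions, and none is described for usual care before surgery. After surgery, capture common to both arms is limited to consults whose findings are not said to be logged and to severe complications. Some comparison of pain and severe post-surgical events remains possible. For other events the safety hypothesis and the Appendix 2 count have no background rate collected in the same way.

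The size depends on what is counted. At the documents' incarceration rates the chance that background alone reaches the two-event tier among 15 participants is under 1%. At assumed background rates of 5% to 20% for any event it is 17% to 83%. The consequence is a safety progression criterion that is hard to interpret, not a wrong statistical test. The conclusion assumes that the attachments do not already provide for control-arm enquiry. It is a cheap improvement that should be made.

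**What to change.** **In section 2.1, Safety and adverse effects:**

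1. Give both arms the event items of the existing Adherence and Adverse Events Form through REDCap at common time points: at least the before-surgery assessment and 1 week, 1 month and 3 months after surgery. If the attached timeline already does this, say so here.
2. Record events found at the surgeon consults as study events in both arms.
3. Keep the weekly enquiry in the intervention arm, but list separately any events found only there or at the extra surgeon assessment.

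**In Plan for Data Analysis:** report events by arm and by phase (before and after surgery) with denominators, and base any between-arm safety statement on the common time points only.

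**In Appendix 2:** state that the adverse-event count refers to intervention-arm events, and reconcile it with the serious adverse events named under Measures. Without this, the added control events could inflate the count.

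**Cost:** one short form on a system already used for the questionnaires, a few sentences of text, and slightly more questionnaire contact for 15 controls. The between-arm comparison should be presented as descriptive.

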2.2 Research Methods and Procedures

Some research methods prompt specific ethical issues. The methods listed below have additional questions associated with them in this application. If your research does not involve any of the methods listed below, ensure that your proposed research is adequately described in Section 2.1: Study Objectives and Design or attach documents in the Documentation Section if necessary.

* This study will involve the following(select all that apply)
Surveys and Questionnaires (including internet surveys)

NOTE 1: Select this ONLY if your application SOLELY involves a review of paper charts/electronic health records/administrative health data to answer the research question. If you are enrolling people into a study and need to collect data from their health records in addition to other interventions, then you SHOULD NOT select this box.

NOTE 2: Select this option if this research ONLY involves analysis of blood/tissue/specimens originally collected for another purpose but now being used to answer your research question. If you are enrolling people into the study to prospectively collect specimens to analyze you SHOULD NOT select this box.

2.9 Surveys and Questionnaires (including Online)

1.0 How will the survey/questionnaire data be collected (i.e. collected in person, or if collected online, what survey program/software will be used etc.)?

If participants are unable to complete study questionnaires on REDCAP, we will provide paper copies. But this will not be based on preference. We will complete as much as possible using REDCAP to minimize contact due to COVID-19.

2.0 Where will the data be stored once it's collected (i.e. will it be stored on the survey software provider servers, will it be downloaded to the PI's computer, other)?

Data will be downloaded and stored on the Co-Principal Investigators' computers.

3.0 Who will have access to the data?

The Co-Principal investigators and any graduate students supervised by the Co-PIS working on this project will have access to the data.

4.0 If you are using a third party research tool, website survey software, transaction log tools, screen capturing software, or masked survey sites, how will you ensure the security of data gathered at that site?

3.1 Risk Assessment

1.0 * Provide your assessment of the risks that may be associated with this research:

Minimal Risk - research in which the probability and magnitude of possible harms implied by participation is no greater than those encountered by participants in those aspects of their everyday life that relate to the research (TCPS2)

2.0 * Select all that might apply:

Description of Possible Physical Risks and Discomforts

Yes Participants might feel physical fatigue, e.g. sleep deprivation

Yes Participants might feel physical stress, e.g. cardiovascular stress tests

Yes Participants might sustain injury, infection, and intervention side-effects or complications

Yes The physical risks will be greater than those encountered by the

participants in everyday life

Possible Psychological, Emotional, Social and Other Risks and Discomforts

Participants might feel psychologically or emotionally stressed,
demeaned, embarrassed, worried, anxious, scared or distressed, e.g.
description of painful or traumatic events

Possibly Participants might feel psychological or mental fatigue, e.g intense concentration required

Possibly Participants might experience cultural or social risk, e.g. loss of privacy or status or damage to reputation

No Participants might be exposed to economic or legal risk, for instance non-anonymized workplace surveys

Possibly The risks will be greater than those encountered by the participants in everyday life

* Provide details of all the risks and discomforts associated with the research for which you indicated YES or POSSIBLY above.

Since the Prehab program involves physical exercise by the participants, there is an inherent element of physical risk. This may involve fatigue, tiredness, physical stress or injury, or other related complications. The Prehab program is in addition to usual care and typically patients with inguinal hernia do not participate in physical exercise prior to undertaking surgery. However, the program comes with several potential benefits that will be discussed.

Specific physical complications could arise before the operation is performed or after surgery. Prior to surgery, the patient may experience more pain in the hernia site as well as normal pain associated with exercise, they may notice worsening of the size of the hernia, and there is a very small chance of hernia incarceration (i.e. herniated tissue becomes trapped and cannot easily be moved back into place – typically occurs in less than 1% (0.18% to 0.79%) of hernia cases). Increased symptoms or size of the hernia will be monitored, and exercises will be modified if the symptoms become intolerable to the participant. Hernia incarceration is an acute painful episode that will require a visit with the surgeon.

In the post-operative phase, patients may experience postoperative pain, opening of the superficial wound from potential hazards associated with exercising (i.e. falling, etc.). However, studies on the force required to cause hernia rupture indicate the force is quite high and beyond those generated during the exercises prescribed. If a participant experiences pain associated with our exercise intervention, we will modify or stop the aggravating exercises after consultation with the surgeon.

Exercise prior to surgery requires mental concentration and participants may feel psychologically or emotionally stressed or fatigue. Since they are in a research study, there is always some risk of social risk through loss of privacy.

4.0 * Describe how you will manage and minimize risks and discomforts, as well as mitigate harm:

The exercise programs will be monitored by experienced physical therapists and kinesiologists who will track patient progress. Since the exercise program is overall low intensity exercise, we do not anticipate many injuries or adverse events. However, if patients begin experiencing problems, the therapists will advise on alterations to make the exercises less intensive or recommend that the program be stopped. The therapists will also be available should more serious adverse events occur such as injury or other related complication. If this occurs, the therapists will advise on self-management strategies for the injury or initiate follow-up with the surgeon.

5.0 Is there a possibility that your research procedures will lead to unexpected findings, adverse reactions, or similar results that may require follow-up (i.e. individuals disclose that they are upset or distressed during an interview/questionnaire, unanticipated findings on MRI, etc.)?

Tes ONO		Yes	0	No
---------	--	-----	---	----

Describe the arrangements or referral the researcher will make. Explain if no arrangements have been made.

As mentioned above, the participants will be monitored by experienced physical therapists and kinesiologists that can provide advice or take immediate action. The general surgeon on our team who are helping to recruit patients will also be available to consult on any serious adverse reactions.

6.0 If you are using any tests in this study diagnostically, indicate the member(s) of the study team who will administer the measures/instruments:

Test Test Organization Administrator's Administrator

There are no items to display

7.0 If any research related procedures/tests could be interpreted diagnostically, will these be reported back to the participants and if so, how and by whom?

Not applicable as the measures we are using track patient progress only. They are not interpreted diagnostically.

If the surgeon believes an ultrasound imaging scan is needed to detect reof the hernia, this will be done in the context of usual care and results will be reported to the patients.

